4.4.1.6 VISIT 4: STUDY EXIT

Visit 4 is completed when the participant exits the study. This may occur after study completion (i.e. after Visit 3), or if the participant discontinues from the study. The following procedures will be conducted at this visit:

- Remove study lenses
- Ocular health assessment*
- Visual acuity with habitual spectacles or refraction (high contrast, high illumination)
- Study completion or discontinuation form (as appropriate)
- Remuneration form

*These procedures are not required if Visit 4 is concurrent to a visit where an ocular health assessment has already been conducted.

4.4.2 UNSCHEDULED VISITS

An unscheduled visit is defined as an interim visit requested by the participant or investigator due to an unanticipated problem. Data recorded at these visits will be entered into the database. Only relevant and applicable unscheduled visit information will be included in the final report as deemed necessary by the lead investigator.

4.5 STUDY PROCEDURES

Table 3 summarizes all the study procedures that are conducted in this study.

Table 3: Summary of procedures to be conducted at scheduled visits

Procedure	1	1A	1B	2	3	4
Informed consent	X					
Demographics (including contact lens history, wear schedule, medical history)	X					
*Changes to health and medication		X	X	X	X	
LogMAR visual acuity (high illumination, high contrast)	X	X	X	X	X	X
Subjective refraction	X					
Auto-refraction and keratometry	X					
Study lens optimized fitting (Proclear 1 Day and Clariti 1 Day)	X					
*Dispense study lenses		X		X		
Spherical over-refraction with contact lenses	X					
Study lens fit assessment	X	X	X	X	X	
████████████████████	■		■	■	■	
████████████████████				■		
████████████████████					■	
████████████████████					■	
████████████████████	■					
*Biomicroscopy	X	X	X	X	X	

*Procedure not required if visit immediately follows another visit

4.5.1 DEMOGRAPHICS

Demographic information will be obtained from the participant, including: age, gender, contact lens history, wear schedule, use of rewetting drops and relevant health and medical information. Medical history questions to determine any medical conditions, prior/concomitant medications and allergies will be asked and documented.

4.5.2 LOGMAR VISUAL ACUITY

Distance logMAR visual acuity will be measured using high contrast computer-generated acuity charts in high illumination room lighting. Participants will be asked to read letters with the study lenses, their glasses and their refraction that progressively decrease in size on a computer screen at a viewing distance of 6 metres.

4.5.3 AUTO-REFRACTION AND KERATOMETRY

Automated refraction and keratometry measurements will be taken to determine the participant's approximate spectacle refraction.

4.5.4 SUBJECTIVE REFRACTION

A subjective sphero-cylindrical distance refraction will be conducted with the participant viewing letters at the computer-generated logMAR visual acuity chart at a viewing distance of 6 metres.

4.5.5 STUDY LENS OPTIMIZED FITTING (PROCLEAR 1 DAY AND CLARITI 1 DAY)

The overall fit of Proclear 1 Day (habitual or new fitting) and Clariti 1 Day will be assessed for the following, after at least 2 minutes settling time:

- Lens wettability (0-4, 0.25 steps, where 0 = excellent, 4 = very poor)
- Lens deposition (0-4, 0.5 steps, where 0 = no deposits, 4 = deposits \geq 0.5mm or film > 75% of surface)
- Decentration (optimum / decentration acceptable / decentration unacceptable)
- Corneal coverage in primary gaze (yes / no)
- Post-blink movement (0-4, 1 step, where 0 = insufficient, unacceptable movement, 2=optimal movement, 4=excessive, unacceptable movement)
- Tightness on push-up (0-100%, 5% steps, where 0% = falls from the cornea, 50% = optimum, 100% = no movement)
- Overall fit acceptance (0-4, 1 step, where 0 = should not be worn, 4 = perfect), providing a reason if Grade 2 or less

4.5.5.1 SPHERICAL OVER-REFRACTION WITH CONTACT LENSES

A spherical over-refraction will be conducted during the fitting of Proclear 1 Day and Clariti 1 Day for each eye to optimize the power of the lenses. Distance logMAR visual acuity will be recorded with the over-refraction. If the need to change lens power is found, a new lens with the appropriate power will be obtained. Distance logMAR visual acuity will be reassessed and a spherical over-refraction will be conducted.

4.5.6 STUDY LENS FIT ASSESSMENT

The study lenses will be assessed for the following during the lens fit assessment at Visit 1B and Visit 3:

- Lens wettability (0-4, 0.25 steps, where 0 = excellent, 4 = very poor)
- Lens deposition (0-4, 0.5 steps, where 0 = no deposits, 4 = deposits \geq 0.5mm or film > 75% of surface)

- Decentration (optimum / decentration acceptable / decentration unacceptable)
- Corneal coverage in primary gaze (yes / no)
- Post-blink movement (0-4, 1 step, where 0 = insufficient, unacceptable movement, 2 = optimal movement, 4 = excessive, unacceptable movement)
- Tightness on push-up (0-100%, 1% steps, where 0% = falls from the cornea, 50% = optimum, 100% = no movement)
- Overall fit acceptance (0-4, 1 step, where 0 = should not be worn, 4 = perfect), providing a reason if Grade 2 or less

[Redacted]

[Redacted]

[Redacted]

[Redacted]

[Redacted]

[Redacted]

[Redacted]

[Redacted]

[REDACTED]

[REDACTED]

[REDACTED]

[REDACTED]

[REDACTED]

[REDACTED]

[REDACTED]

[REDACTED]

[REDACTED]

[REDACTED]

[REDACTED]

[REDACTED]

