3 HYPOTHESIS

The null hypothesis for this study is that there is no difference in lens fit performance between Proclear 1 Day (omafilcon A) and Clariti 1 Day (somofilcon A) lenses.

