4.2.3 INCLUSION AND EXCLUSION CRITERIA

A person is eligible for inclusion in the study if he/she:

1. Is at least 17 years of age and has full legal capacity to volunteer;
2. Has read and signed an information consent letter;
3. Is willing and able to follow instructions and maintain the appointment schedule;
4. Habitually wears soft spherical contact lenses with a power between +6.00 to -10.00D (inclusive) for a minimum 5 days per week, 10 hours per day **and** anticipates no difficulty wearing contact lenses for 7 days per week, 10 hours per day;
5. Habitually wears, or is able to be adequately refit into Proclear 1 Day lenses;
6. Demonstrates an acceptable fit with Proclear 1 Day and Clariti 1 Day contact lenses;
7. Is correctable to a visual acuity of 0.20 LogMAR (approximately 20/30) or better (in each eye) with the study lenses or habitual correction;
8. Manifest cylindrical spectacle refraction does not exceed -1.00DC in either eye.

A person will be excluded from the study if he/she:

1. Is participating in any concurrent clinical research study;
2. Has any known active* ocular disease and/or infection;
3. Has a systemic condition that in the opinion of the investigator may affect a study measure;
4. Is using any systemic or topical medications that in the opinion of the investigator may affect a study measure;
5. Has known sensitivity to the diagnostic pharmaceuticals to be used in the study;
6. Is pregnant, lactating or planning a pregnancy at the time of enrolment (by verbal communication);
7. Is aphakic;
8. Has undergone refractive error surgery;
9. Is an employee of the Centre for Contact Lens Research;
10. Has taken part in another clinical or (pharmaceutical) research study within the last 7 days.

* For the purposes of this study, active ocular disease is defined as infection or inflammation which requires therapeutic treatment. Mild (i.e. not considered clinically relevant) lid abnormalities (blepharitis, meibomian gland dysfunction, papillae), corneal and conjunctival staining and dry eye are not considered active ocular disease. Neovascularization and corneal scars are the result of previous hypoxia, infection or inflammation and are therefore not active.

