11 STATISTICAL ANALYSIS AND DATA MANAGEMENT

11.1 STATISTICAL ANALYSIS

All data will be analyzed by the CCLR at the University of Waterloo. Unmasked data analysis will be conducted using Statistica 12 and/or SPSS 24. Descriptive statistics will be provided on information regarding baseline variables (age, gender, refractive error distribution, etc.). For data completed on each eye individually (e.g. biomicroscopy), results of the right eye will be reported unless a difference between right eye and left eye is found. Table 4 lists the primary outcome variables and anticipated statistical procedures.

Table 4 : Statistical procedures

Variable	Analysis	Statistical test
Numeric rating scales Visual acuity Lens fitting Biomicroscopy (continuous variables)	Effect of lens type	Paired t-test Wilcoxon matched pairs test
Biomicroscopy (ordinal variables)	Effect of lens type	Friedman Wilcoxon matched pairs test
Subjective preference ratings Investigator refit agreement ratings	Preference of lens type	Binomial test

All data will be tested for normality of distribution using Shapiro-Wilk tests. The appropriate statistical test will be selected based on tests of normality. Statistical significance will be set at 5%, with no adjustments for multiple comparisons. In the event of missing data, individual data points will be excluded in the analysis and not extrapolated from the collected data.

A binomial test will be used to analyze the results for the count data of subjective preferences and investigator refit agreement ratings. The number of “no preference” (if featured on the scale) will be evenly distributed to the two options on the basis respondents would be equally likely to choose either.

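### Two lens-fit items are best at mid-scale, but the planned paired test on their recorded scores shows looser versus tighter, not better versus worse

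*Combined protocol and SAP*

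**What the plan says.** Section 2 names lens fit as one of two primary outcomes. The null hypothesis in section 3 is that "there is no difference in lens fit performance between Proclear 1 Day (omafilcon A) and Clariti 1 Day (somofilcon A) lenses".

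Section 4.5.6 lists seven fit items, assessed at Visits 1B and 3. Two have a mid-scale optimum:

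- The first is a five-grade item: "Post-blink movement (0-4, 1 step, where 0 = insufficient, unacceptable movement, 2 = optimal movement, 4 = excessive, unacceptable movement".
- The second is a percentage item, again with its best value halfway along: "Tightness on push-up (0-100%, 1% steps, where 0% = falls from the cornea, 50% = optimum, 100% = no movement".

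An overall grade in the same list runs in one direction: "Overall fit acceptance (0-4, 1 step, where 0 = should not be worn, 4 = perfect), providing a reason if Grade 2 or less".

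Section 11.1, Table 4, places lens fitting in a single row, "Numeric rating scales Visual acuity Lens fitting Biomicroscopy (continuous variables", against "Paired t-test Wilcoxon matched pairs test". The only rule for choosing between the two tests is "The appropriate statistical test will be selected based on tests of normality". Section 11.1 gives no distance from optimum, no acceptable/unacceptable split, and no rule for reading the sign of a difference on the two mid-optimum items.

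**The concern.** A paired t-test or Wilcoxon test on recorded scores asks whether one lens scores systematically higher than the other. For overall fit acceptance, that is the same as asking which lens fits better. For movement and tightness it is not, because a higher score is better below the optimum and worse above it. Two misreadings follow:

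- **False reassurance.** If one lens leaves more eyes off optimum, some too loose and some too tight, the signed differences cancel. A non-significant result could then be reported as equal fit performance.
- **False alarm, or wrong direction.** A significant shift shows that one lens sits looser or tighter. It does not show that it fits worse. Tightness moving from 40% to 50% (towards the optimum) and from 50% to 60% (away from it) both give a difference of +10.

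Both items belong to a primary outcome and feed the stated hypothesis, so the reading matters.

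**Working it through.** **Inputs from the documents.** The optima are 2 (movement) and 50% (tightness), from section 4.5.6. The tests and the 5% level come from section 11.1; two-sided testing is assumed because sidedness is not stated. The completing sample is n = 67 (sections 4.2.1 and 4.2.2). Section 4.2.1 sizes the study for a 7-unit comfort difference at 80% power and gives no SD, so 67 cannot be reproduced directly. A two-sided paired t-test implies a standardised difference of 0.347, hence an SD of differences of 7/0.347 = 20.2. That says nothing about power for lens fit; only n is used here.

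**Exact example.** Suppose lens A is at grade 2 in all of 66 eyes, and lens B is at grade 1 in 33 and grade 3 in 33. The mean signed difference is (33 × (−1) + 33 × (+1))/66 = 0, and both planned tests give p = 1.0. The mean change in |score − 2| is 66/66 = 1 grade: every eye has left the optimum.

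**Formula.** With independent draws, approximate power is Φ(z − 1.96), where z = Δ√67/√(V₁ + V₂) and √67 = 8.185. Δ is the difference in means and V₁, V₂ are the variances, taken either on the score or on its distance from optimum. Percentages below are for grades 1/2/3.

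- *Even split, 5/90/5 to 15/70/15.* Signed: Δ = 0, so about 5%. Distance: Δ = 0.30 − 0.10 = 0.20; V₁ + V₂ = 0.10 × 0.90 + 0.30 × 0.70 = 0.30; z = 0.20 × 8.185/0.548 = 2.99; power about 85%.
- *2:1 split, 5/90/5 to 10/70/20.* Signed: Δ = 0.10; V₁ + V₂ = 0.10 + (0.30 − 0.01) = 0.39; z = 0.10 × 8.185/0.624 = 1.31; power about 26%.
- *Mainly one way, 10/80/10 to 3/70/27.* Signed: Δ = 0.24; V₁ + V₂ = 0.20 + (0.30 − 0.058) = 0.442; z = 0.24 × 8.185/0.665 = 2.95; power about 84%.

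**Simulation.** 3,000 replicates per scenario, two-sided 5%. All distributions are assumed. Movement is limited to grades 1 to 3 because the entry criterion "Demonstrates an acceptable fit with Proclear 1 Day and Clariti 1 Day contact lenses" makes 0 and 4 unlikely. Square brackets give results with a latent correlation of 0.5 between lenses. For movement the t and Wilcoxon results agree within 0.2 points. Tightness is drawn normal, rounded to 1%, and tested by Wilcoxon.

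| Scenario | Signed score rejects | Distance from optimum rejects |
|---|---|---|
| Movement, off-optimum 10% to 30%, even | 4.9% [5.1%] | 83.5% [88.7%] |
| Movement, 10% to 20%, even | 4.7% [5.2%] | 36.5% [41.4%] |
| Movement, 20% to 30%, even | 5.1% [5.3%] | 27.0% [30.9%] |
| Movement, 10% to 30%, split 2:1 | 26.5% [33.5%] | 84.0% [89.2%] |
| Movement, mainly one way (10/80/10 to 3/70/27) | 83.8% | 28.5% |
| Movement, mirror image (25/70/5 to 5/70/25) | 99.5% | 5.6% |
| Tightness, mean 50, SD 5 to 7.5 | 5.2% | 78.8% |
| Tightness, mean 50, SD 5 to 6 | 4.8% | 24.1% |
| Tightness, mean 50 to 53, SD 5 | 91.2% | 19.8% |
| Null check (10/80/10 in both lenses) | 4.3% | 4.9% |

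**Protection from overall fit acceptance, first scenario.** The grade is modelled as 4 minus |score − 2|, tested by Wilcoxon. It rejects in 84% of trials if every off-optimum eye loses a grade and nothing else affects the grade. It rejects in 50% if 20% of lenses also lose a grade for other reasons, 47% if only half of off-optimum eyes are marked down, and 20% if both apply.

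Repeat runs of the independent-draw scenarios agreed within 4 points.

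**The case against.** Five points can be made for the plan.

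1. **Off-optimum is not the same as unacceptable.** The movement scale calls only 0 and 4 unacceptable, and the entry criterion screens for acceptable fit. This limits the clinical weight of the scenarios. Still, grades 1 and 3 are non-optimal on the plan's own scale, and the null concerns performance, not acceptability alone.
2. **A one-way shift may be the likelier pattern.** Each lens comes in one base curve and diameter (Table 1: 8.6/14.1 versus 8.7/14.2). With 0/90/10 to 0/70/30 both tests reject in 85.1% of trials. With 5/90/5 to 2/70/28 the signed test does better, 96.0% against 86.1%. This stands. The documents do not show which pattern to expect, which is a reason to keep both comparisons.
3. **Overall fit acceptance already answers better or worse**, with a reason required at low grades. This stands in part. The protection depends on how closely the grade follows movement and tightness, which the plan does not say, and the plan does not name it as the deciding item.
4. **Table 4 lists only anticipated procedures, and per-lens summaries would show the side of the optimum.** True, but the study is open label (section 4.1.3) and analysed unmasked (section 11.1). A recoding chosen after the results are seen would be open to challenge.
5. **The remedy has its own costs.** Distance from optimum treats equal looser and tighter deviations as equally bad, which the documents do not establish. Running both tests unadjusted also gives at least one rejection in about 10% to 11% of null trials. The first is a fair caveat to state. The second does not affect the performance claim if that claim rests on the distance test alone.

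**Conclusion.** The concern holds for two of the seven fit items and should be corrected before analysis. As written, the test on post-blink movement and push-up tightness compares direction, while the hypothesis is about performance. With evenly two-sided deviations the planned test stays at its 5% error rate whatever the loss of fit. For a mainly one-way shift it remains the stronger test of the two.

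The rejection rates rest on assumed distributions and show a range, not a forecast. That the plan omits any recoding or reading rule for these items rests on its text alone. The point does not extend to the whole lens-fit outcome: wettability, deposition and overall fit acceptance run from better to worse and can be read directly. A significant signed shift is still a real difference in fit; it just does not show which lens fits worse.

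**What to change.** In Table 4:

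- Add a paired Wilcoxon comparison of |score − 2| for post-blink movement and of |score − 50| for push-up tightness. Name these as the measure of fit performance on the two items, and state that looser and tighter deviations are weighted equally.
- Keep the planned signed comparison, and interpret it only as looser versus tighter.
- Tabulate, for each lens, the number of eyes with movement grade 0 or 4.
- State that both items will be read alongside overall fit acceptance.

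The cost is two derived variables, one extra p-value per item and two lines in Table 4, with no new data, visits or participants. The distance comparison has lower power than the signed one for a mainly one-directional shift, which is why both are kept.

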4.5.11 BIOMICROSCOPY

A slit lamp biomicroscopy examination will be conducted to assess anterior segment ocular health. Ocular findings will be graded using the BHVI grading scale (0-4, 0.25 steps – unless otherwise stated):

- External adnexa anomalies (absent / present & describe)
- Hyperemia:

- Overall bulbar
- Overall limbal
- Corneal examination:
 - Scars or other corneal observations (absent / present & describe)
 - Infiltrates (absent / present & number, size, depth)
 - Sectoral corneal staining with fluorescein (type and extent [using CCLR 0-100 scale, 1 step] and depth [0-4, 1 step])
- Overall conjunctival staining and indentation (0-4, 0.5 steps)
- Palpebral conjunctiva:
 - Hyperemia
 - Roughness

5 MONITORING PROTOCOL ADHERENCE

Adherence to study visit windows, lens wearing schedule and time windows around other data collection points (e.g. subjective ratings) will be monitored internally by the CCLR. Deviations from the windows described in the protocol will be reported in the final study report. Major protocol deviations will be reported to the Sponsor and the University of Waterloo's Office of Research Ethics (ORE) within 7 days of becoming aware of them (as per ORE's guidelines).

6 POTENTIAL RISKS AND BENEFITS TO HUMAN PARTICIPANTS

This is a minimal risk study because of the use of marketed products and standard optometric assessments.

Contact lenses in this study will be worn on a daily wear basis. Adverse events and/ or complications in daily wear of soft contact lenses can occur (e.g. inflammation and infection). When contact lenses are worn on a daily wear basis there is a small risk of an adverse event compared to not wearing contact lenses. When contact lenses are worn on an extended wear basis, there is a significantly increased risk of an adverse reaction compared with wearing contact lenses on a daily wear basis.

It is possible that participants may experience temporary discomfort associated with the study procedures or products including: burning and stinging, blurred vision, sandiness or grittiness, light sensitivity, dryness, itching, crusty eyes and foreign body sensation.

A dye (fluorescein) normally used for eye exams will be used in this study. Although rare, it is possible that participants may have an allergic reaction to the dye. This could cause discomfort to

their eye. Participants are advised to inform the investigator of any sensitivities to any ophthalmic drops or study products.

Participants may not benefit directly from taking part in this study. Information from this study may help researchers come up with new soft contact lenses to help others in the future. In addition, participants will receive an examination of the anterior eye and may have the opportunity to try different types of soft contact lenses at no cost to them. This study may help the study sponsor to better understand the performance of the products being used in this study.

7 ADVERSE EVENTS

An 'adverse event' refers to any undesirable clinical occurrence in a participant, whether it is considered to be device-related or not. Adverse events (AE) may be classified as 'unanticipated adverse device effects,' 'serious adverse events,' 'significant adverse events,' or 'non-significant adverse events,' as defined below.

A number of conditions may result in temporary discontinuation until resolution. These include corneal infiltrates, corneal staining, limbal injection, bulbar injection or bulbar and tarsal conjunctival abnormalities.

See CCLR SOP012_v01 for a description of adverse events, including management and reporting (Appendix 24).

Classification	Definition
Serious Adverse Event	Those events that are life-threatening, or result in permanent impairment of a body function, or permanent damage to a body structure or necessitate medical (therapeutic) or surgical intervention to preclude permanent impairment of a body function or permanent damage to a body structure.
Significant Adverse Event	Those non-serious adverse events that occur with contact lens usage that are not sight-threatening but are usually symptomatic and may warrant therapeutic management and /or temporary or permanent discontinuation of contact lens wear.
Non-Significant Adverse Events	Those less severe non-serious adverse events that occur with contact lens usage that are not sight-threatening, may or may not be symptomatic and may warrant palliative management, such as ocular lubricants or temporary interruption of contact lens wear.
Unanticipated Adverse Device Effect	Adverse events in a study that were not previously identified in the protocol in terms of nature, severity, or degree of incidence. An Unanticipated Serious Adverse Device Effect is an unanticipated adverse event that is serious in nature and caused by or associated with the device and is considered reportable.

AE classification, coding (for reporting to the sponsor) and examples are provided in the following table of Contact Lens Adverse Event Classification and Reporting table:

Code	Condition	Reporting
Serious Adverse Events		
01	Presumed infectious keratitis or infectious corneal ulcer	For all serious AEs: Notify sponsor as soon as possible, within 24 hours; ORE reporting will be within 24 hours as per requirements
02	Permanent loss of ≥ 2 lines of best spectacle corrected visual acuity (BSCVA)	
03	Corneal injury that results in permanent opacification within central cornea (6mm)	
04	Uveitis or Iritis (e.g. presence of anterior segment inflammation as described in ISO 11980, Annex B)	
05	Endophthalmitis	
06	Hyphema	
07	Hypopyon	
08	Neovascularization within the central 6mm of cornea	
00	Other serious event	
Significant Adverse Events		
11	Peripheral (outside central 6mm), non-progressive, non-infectious ulcer	Notify sponsor as soon as possible, within 5 working days; ORE reporting as per requirements
12	Symptomatic corneal infiltrative event	
13	Superior epithelial arcuate lesions (SEALs) involving epithelial split	
14	Corneal staining \geq dense coalescent staining up to 2mm in diameter (e.g. moderate, ISO 11980 grade 3)	
15	Corneal neovascularization ≥ 1.0 mm vessel penetration (e.g. \geq ISO 11980 Grade 2), if 2 grade change from baseline	
16	Any temporary loss of ≥ 2 lines BSCVA for ≥ 2 wks	
17	Any sign and/or symptom for which participant is administered therapeutic treatment or which necessitates discontinuation of lens wear for ≥ 2 weeks	
10	Other significant event	
Non-significant Adverse Events		

21	Conjunctivitis (bacterial, viral or allergic)	Notify sponsor as soon as possible, within 5 working days ; ORE reporting as per requirements
22	Papillary conjunctivitis if \geq mild scattered papillae/follicles approximately 1mm in diameter (e.g. ISO 11890 Grade 2), if 2 grade change from baseline	
23	Asymptomatic corneal infiltrative events	
24	Any sign and/or symptom for which temporary lens discontinuation for > 1 day is recommended (if not already classified)	
20	Other sign and/or symptom warranting classification as a non-significant adverse event	

